 - a. Severity/Amplitude: As measured by the MDS-UPDRS tremor subscore.
 - b. Limb function: As measured by the Action Research Arm Test (ARAT)
2. Evaluate Px1 versus expert clinical assessment and its sensitivity to detect changes based on the MDS-UPDRS tremor subscore
3. Determine whether methodology for this pilot project can feasibly be applied to a larger subsequent study that could be adequately powered to detect a clinically-meaningful effect of onabotulinumtoxin A on medically-refractory rest tremor.

ii. **Hypotheses:**

1. (A) Onabotulinumtoxin A significantly attenuates the amplitude of medically-refractory rest tremor of the upper limb in Parkinson's patients as compared to sham injections; as measured by reduction in the MDS-UPDRS tremor subscore.
1. (B) Onabotulinumtoxin A significantly improves the limb function of Parkinson's patients with medically-refractory rest tremor of the upper limb as compared to sham injections; as measured by an increase in ARAT scores.

III. Subjects

i. **Pilot group**

- **Number – 16**
 - Due to the limitations brought on by internal funding for this pilot project and the overall cost of botulinum toxin, an even number of patients was chosen after a cost analysis was completed. It was determined that we could cover the cost of 16 participants throughout the proposed course of the study.
- **Gender** – male or female
- **Ethnicity** – all, no restrictions
- **Race** – all, no restrictions
- **Age** – 45-80

ii. **Eligibility Criteria**

Inclusion Criteria:

1. At least 45 years of age, and no more than 80 years of age.
2. Meet UK Parkinson's disease brain bank diagnostic criteria
3. Have clinical evidence of rest tremor of one or both upper extremities defined as involuntary, rhythmic oscillations about any joint within the upper extremities
4. Rest tremor amplitude must be at minimum 3 cm as determined by expert opinion by a movement disorders specialist. Confirmation of amplitude measurement will

be obtained from the Px1 prior to active participation in the study but will not be used for inclusion/exclusion in study participation.

5. Rest tremor must be historically refractory to at least 2 categories of medications typically used as anti-parkinsonian agents including levodopa formulations, dopamine agonists, amantadine, and anticholinergics.
6. **Determining Medication Refractoriness:**

AFTER patient is consented:

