No power calculation can be performed. This is a pilot feasibility study to determine if onabotulinumtoxin A can be utilized to reduce resting tremor amplitude and improve arm function.

Data Analysis (Performed by [name], PhD)

Note that all statistical analysis, and as such any missing data/values/dropouts, will be performed assuming an intention-to-treat principle. All statistical estimates will be tabulated along with corresponding confidence intervals (CIs). All hypothesis tests that are observed to be not statistically significant will be reported as being inconclusive. Lastly, all data acquired for Visit 5 will be utilized for review of safety. This is to ensure that the expected washout effect is occurring and that there is expected normalization of values trending towards or back to previous baseline values. For this reason, there is an absence of any testing with the Px1 on Visit 5 (since data will not be utilized to compare to previous visits for purposes of statistical analysis).

Specific Aim 1a. The change in tremor severity effected by onabotulinumtoxin A will be compared to the change effected by sham saline. Tremor severity will be measured via the MDS-UPDRS tremor subscore. A Student's t-test will be utilized to compare postintervention measures within subjects.

Specific Aim 1b. The change in limb function as measured by the ARAT created by onabotulinumtoxin A will be compared to the change created by sham saline. A Student's t-test analysis will be used to compare change in ARAT scores within subjects.

Specific Aim 2. The strength of the correlation between MDS-UPDRS tremor subscore and tremor characteristics as assessed by the Px1 will be obtained. Will then evaluate the strength of the correlation between the change in MDS-UPDRS score and change in the ARAT score. This latter correlation will then be compared to the correlation between the change in tremor characteristics as assessed by the Px1 and the change in the ARAT score.

Specific Aim 3. Pilot data will be reviewed and trends analyzed. Subsequent power analysis will be performed to determine size of study population that is necessary to adequately measure statistically significant effect. Data regarding dropout rates will also be reviewed to determine if study methodology needs to be adjusted for a larger study population.

Interpretation of Results

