Specific Aim 1a. A reduction in severity/amplitude of the rest tremor by onabotulinumtoxin A greater than the change in severity/amplitude from sham saline injections suggests that onabotulinumtoxin A may be superior to sham saline injections in reducing severity of medically-refractory rest tremor and will be used as preliminary data for future grant proposals for larger, more rigorous studies. Failure to demonstrate this difference would suggest one or more of several possibilities: (1) that the doses of onabotulinumtoxin A were too low to lead to a measurable effect, and/or (2) onabotulinumtoxin A does not show promise as an intervention to reduce rest tremor amplitude compared to sham injections and should not be further studied for this purpose. The information gathered from this pilot project could then be utilized to (1) postulate higher dose delivery to reach an effect, and/or (2) choose alternative botulinum toxins that might produce an effect on tremor as compared to onabotulinumtoxin A. Using these variables, a subsequent study could be designed.

Specific Aim 1b. A greater increase in score on the ARAT after onabotulinum toxin injection compared to after sham saline injections suggests that onabotulinumtoxin A may provide clinically-meaningful improvement on the interruption caused by rest tremor on activities of daily living, and this preliminary data will be used for future grant proposals for larger, more rigorous studies. Failure to demonstrate this difference would suggest one or more of several possibilities: (1) that the doses of onabotulinumtoxin A were too low to lead to a measurable effect, and/or (2) onabotulinumtoxin A does not show promise as an intervention to improve arm function in the setting of rest tremor as measured by the ARAT, and thus it should not be further studied for this purpose. The information gathered from this pilot project could then be utilized to (1) postulate higher or lower dose delivery to reach an effect, and/or (2) choose alternative botulinum toxins that might produce an effect on tremor as compared to onabotulinumtoxin A. Using these variables, a subsequent study could be designed.

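### Aims 1a and 1b: a failed comparison may be read as grounds for not studying the toxin further, with no mention of imprecision from 16 cost-set patients, although section VI calls non-significant tests inconclusive

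*Combined protocol and SAP*

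**What the plan says.** Four parts of the combined protocol and SAP bear on this.

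- **Section VI, Data Analysis:** "All hypothesis tests that are observed to be not statistically significant will be reported as being inconclusive". The same paragraph requires confidence intervals for all estimates.
- **Section VI, Interpretation of Results, Aims 1a and 1b:** "Failure to demonstrate this difference would suggest one or more of several possibilities". Two possibilities follow, joined by and/or: the doses were too low, or the toxin lacks promise. In Aim 1a the second reads that it "does not show promise as an intervention to reduce rest tremor amplitude compared to sham injections and should not be further studied" for this purpose; Aim 1b says the same of arm function. Each paragraph then names a changed dose or another toxin as ways forward and ends by foreseeing a further study.
- **Sample size:** section III says "It was determined that we could cover the cost of 16 participants throughout the proposed course of the study", and section VI, Power Calculation, says "No power calculation can be performed".
- **Aim 3:** section II looks to a "larger subsequent study that could be adequately powered to detect a clinically-meaningful effect of onabotulinumtoxin A", and section VI plans to size it: "Subsequent power analysis will be performed to determine size of study population that is necessary to adequately measure statistically significant effect".

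**The concern.** Inconclusive and not worth further study are different messages, and the plan appears to allow both for the same non-significant result. In a trial sized by budget, imprecision is an obvious explanation for a null result, yet neither list includes it. The follow-on options also leave out the natural next step after an imprecise null, which is the same regimen in more patients.

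At stake is how the pilot is interpreted and cited. A null result could be used to close a question that the trial was not sized to answer. No data, endpoint, test or procedure is affected.

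**Working it through.** **No figure to reproduce.** The plan states no power, alpha, SD, target difference or dropout rate. The calculation below only illustrates whether imprecision is a material explanation.

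**Inputs from the documents.** 16 patients (section III); a crossover with a within-subject Student's t-test for Aims 1a and 1b (section VI, Data Analysis), taken here as a paired t-test.

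**Assumptions.** Two-sided 5%; normally distributed differences; 16, 14 or 12 complete pairs; true benefit *d* in SDs of the within-subject difference.

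**Step 1: what counts as failure.** The Aim 1a and 1b paragraphs refer back to a larger reduction, or a larger increase, than with sham, and do not mention significance. The Aim 2 paragraph does. On the other hand, the hypotheses in section II are worded in terms of significant effects, and the Data Analysis rule on non-significant tests stands just before these paragraphs. Both readings are possible, so both are worked.

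**Step 2: reading A, failure is a non-significant test.** P(miss) = P(|T| < t(0.975, n−1)), where T is noncentral t with n−1 df and noncentrality d√n. For n = 16 and d = 0.5, the noncentrality is 0.5 × 4 = 2, the critical value is 2.131, and P = 0.535.

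**Step 3: reading B, failure is an estimate no better than sham.** P = Φ(−d√n). For n = 16: Φ(−0.3 × 4) = Φ(−1.2) = 11.5%, and Φ(−0.5 × 4) = Φ(−2) = 2.3%.

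| True effect *d* | A: 16 / 14 / 12 pairs | B: 16 / 14 / 12 pairs |
|---|---|---|
| 0.3 SD | 80% / 82% / 84% | 11.5% / 13.1% / 14.9% |
| 0.5 SD | 54% / 59% / 65% | 2.3% / 3.1% / 4.2% |
| 0.75 SD | 20% / 26% / 34% | under 0.5% |
| 1.0 SD | 4% / 7% / 12% | under 0.5% |

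Under reading A, a simulation of 300,000 trials at n = 16 agrees (0.798, 0.535, 0.199 and 0.038). Using n−2 df, as with a period term, changes power by less than 1 percentage point.

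**Step 4: precision.** The 95% CI half-width is t(0.975, n−1)/√n when the sample SD equals the true SD: 2.131/4 = 0.53 SD with 16 pairs, 0.58 with 14 and 0.64 with 12. The effect detected with 80% power is 0.75, 0.81 and 0.89 SD respectively.

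**Step 5: what a larger sample would do.** For 80% power the same test needs 90 pairs at 0.3 SD, 34 at 0.5 SD and 15 at 0.8 SD. For small and moderate effects, the option missing from the lists is therefore the one that would resolve the question.

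**The case against.** The case against is substantial, and parts of it stand.

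- **Failure is undefined.** This stands. The contradiction, and the high miss rates, hold only under reading A. Under reading B a real benefit seldom counts as failure.
- **The wording is hedged.** This stands. A reader might infer a futility or stopping rule. The text does not support that: it speaks of what a result would suggest, among several possibilities joined by and/or, and prescribes no action.
- **A further study is foreseen.** This stands in part. A reader might infer that the plan drops the question after a failed Aim 1. It does not: the text on a further study directly follows the failure sentence in both paragraphs. But it gets there only through a changed dose or another toxin, not through more patients.
- **Existing safeguards cover it.** The inconclusive label, the CIs and the later power analysis do help. However, the interpretation paragraphs for Aims 1a and 1b do not use them, and nothing says that the CI decides between inconclusive and unpromising.
- **Large effects would be found.** This stands under the stated assumptions. With 16 complete pairs an effect of 1.0 SD is missed about 4% of the time. A reader might infer that the pilot can show nothing; the figures do not say so.

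**Conclusion.** The point holds as a minor inconsistency of interpretation. If failure means non-significance, the Aim 1a and 1b paragraphs conflict with the Data Analysis rule, and effects below about 0.75 SD would be missed more than 20% of the time even with all 16 pairs. If it means an estimate no better than sham, the conflict softens. On either reading, imprecision and a larger sample are absent from lists written for a trial whose size was set by cost.

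The text itself establishes the omission. The percentages rest on the assumed test level, normality and number of complete pairs. Because the documents give neither an SD nor a worthwhile difference, it is unknown which row of the table applies to this trial.

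**What to change.** Edit only the Aim 1a and 1b paragraphs of section VI, Interpretation of Results.

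1. Add to each list of explanations: *and/or (3) insufficient precision with 16 patients*.
2. Delete the closing clause of possibility (2) that advises against further study, in both aims, and put in its place: *A non-significant result is reported as inconclusive with its estimate and CI and is carried into Aim 3 planning; a lack-of-promise reading is reserved for a result whose CI favours sham or excludes a worthwhile benefit.*

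The second sentence part keeps a result against the toxin covered. Excluding a worthwhile benefit can be judged only if that benefit is stated in advance for each scale; the documents give none, so the investigators would have to supply it. If such a CI also includes zero, the test keeps its inconclusive label and the lack-of-promise statement rests on the CI.

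The other listed explanations and follow-on options can stay as they are. The cost is wording, plus stating those two differences. The downside is that more null results will be labelled inconclusive.
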